2.5.2. Safety Laboratory Data

Safety laboratory testing will be performed at Screening, Days 1, 4, 7, 15, 29, 42, or ET visit. The details are listed in below table.

Hematology	Chemistry	Urinalysis	Other
Hemoglobin	Urea and creatinine	Local dipstick:	At screening:
Hematocrit	Serum cystatin C	pH	FSH ^b
RBC count	eGFR	Glucose (qual)	Pregnancy test (β -hCG) ^c
Platelet count	Glucose (fasting)	Protein (qual)	HBsAg and HBcAb.
WBC count	Calcium	Blood (qual)	HBsAb and HBV
Total neutrophils (Abs, %)	Sodium	Ketones	DNA as reflex tests
Eosinophils (Abs, %)	Potassium	Nitrites	Hepatitis C antibody and HCV
Monocytes (Abs, %)	Chloride	Leukocyte esterase	RNA as reflex test
Basophils (Abs, %)	Total CO ₂ (bicarbonate)	Laboratory:	HIV
Lymphocytes (Abs, %)	AST, ALT	Microscopy and culture ^a	HLA genotype and CeD serology (eg, HLA DQ2.5 and HLA-DQ8 testing ^d , tTG and DGP IgA/IgG)
PT	Total and direct bilirubin		Biomarker: IL-2
aPTT	Alkaline phosphatase		PK/ADA
INR	Uric acid		
	Albumin		
	Total protein		
	Magnesium		
	Amylase		
	Lipase		
	Phosphorus		

- a. Only if Urinary Tract Infection is suspected and urine dipstick is positive for nitrites or leukocyte esterase or both.
- b. For confirmation of postmenopausal status only.
- c. A serum pregnancy test is required at screening. Following screening, local urine testing will be standard for the protocol unless serum testing is required by local regulation or IRB/EC. Serum or urine β -hCG for female participants of childbearing potential.
- d. For re-screening, the HLA does not need to be repeated and CeD serology (the tTG and DGP antibody tests) should only be repeated if >3 months have elapsed from end assessment.

2.5.3. Vital Signs

Vital signs will be assessed at Screening, Days 1, 4, 7, 15, 29, 42, or ET visit.

3. ANALYSIS SETS

For purposes of analysis, the following analysis sets are defined:

Analysis Set	Description
Enrolled	All participants who sign the ICD.
Biomarker Analysis Set (BAS)	All participants who are randomly assigned to study intervention, receive any portion of study intervention, and have completed the GC on Day 15, without prohibited medications. Participants will be analyzed according to the intervention they are randomized.
Full analysis set (FAS)	All participants who are randomly assigned to study intervention, receive all 3 doses of study intervention, and complete at least 7 days of the 2-week GC without prohibited medications. Participants will be analyzed according to the intervention they are randomized.

Analysis Set	Description
Per protocol set (PPS)	The PPS will include all participants from the FAS who complete all 14 days of the 2-week GC and biopsies, and without major protocol violations that might affect the evaluation of the effect of study intervention on the primary endpoint. The PPS will be used in sensitivity analyses of the primary and secondary endpoints. Specific reasons for warranting exclusion from this population will be documented prior to database lock.
Safety analysis set (SAS)	All participants who receive any portion of study intervention. Participants will be analyzed according to the intervention they actually received.
PK analysis set (PKAS)	All participants who receive any portion of study intervention and have at least one concentration value.

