### Analysis Population

All participants who receive any portion of study intervention will be included in the Safety Analysis Set. All safety data will be summarized for participants in the Safety Analysis Set.

The Full Analysis Set will consist of all randomized participants who receive all 3 doses of study intervention and complete at least 7 days of GC.

The Per Protocol Set will include all participants from the FAS who complete all 14 days of GC and biopsies (Baseline [Day 1] and Day 29) and without major protocol violations that might affect study intervention on the primary endpoint. The PPS will be used in sensitivity analyses of the primary and secondary endpoints.

The Pharmacokinetic Analysis Set will contain all participants who received any portion of study intervention and have at least one post-dose drug concentration value.

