**Table 1. Schedule of Assessments**

Abbreviations used in this table may be found in Appendix 12 .	Scr.	Treatment Period				Gluten Challenge (Day 15 to 28)			Biopsy	FU	ET	Notes
Visit Identifier	V1	V2	V3	V4	V5	V6	V7	V8	V9	ET		
 
Day relative to start of study intervention (Day 1).
 
See Section 8.4.3 for follow-up AE and SAE assessments.
 
D16 and D21 are phone call visits (See Section 8.1.1) for collection of AEs and concomitant medications.
 

Type (Site or Phone Call)	Site	Site	Site	Site	Site	Phone	Phone	Site	Site	Site		
Study Day (D)	Up to -42 days	D1	D4	D7	D15	D16	D21	D29	D42	ET		
Visit Window (days)						+2	±2	+3	+3			
Safety Assessments												
Serious and non-serious AE monitoring	X	X	X	X	X	X	X	X	X			
 
See Section 8.4 for additional information.
 

Laboratory tests (safety)	X	X	X	X	X			X	X	X		
 
Includes hematology, chemistry, urinalysis, and coagulation. See Appendix 2 for a list of Clinical Laboratory tests to be done. For collection volumes, see the study laboratory manual.
 
Day 1,4, & 7 collection should be done pre-dose (at least 5 minutes prior to infusion). Day 15 collections should be done prior to the GC.
 

Study Intervention Administration and Randomization												
 
See Section 6 for additional information.
 

Randomization		X										
Study Intervention Administration		X	X	X								
 
See Section 6.1.1. Participants will be observed for at least 4 hours in clinic following IV infusion.
 

Additional Blood Samples												
PK blood sample		X		X								
 
PK sampling will be done pre-dose (at least 5 minutes prior to infusion) and end of infusion (+2) minutes. Additional sampling will be done at 2.5 hours (±5 minutes) and 4 hours (±5 minutes) after infusion start.
 

CONFIDENTIAL

CT02-GSOP Clinical Protocol Template Phase 1 2 3 4 (14 April 2023)

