### 9.3. Analysis Sets

For purposes of analysis, the following analysis sets are defined:

Participant Analysis Set	Description
Enrolled	All participants who sign the ICD.
Full analysis set (FAS)	All participants who are randomly assigned to study intervention and receive all 3 doses of study intervention, and complete at least 7 days of GC. Participants will be analyzed according to the intervention they are randomized.
Per protocol set (PPS)	The PPS will include all participants from the FAS who complete all 14 days of GC and biopsies, and without major protocol violations that might affect the evaluation of the effect of study intervention on the primary endpoint. The PPS will be used in sensitivity analyses of the primary and secondary endpoints. Specific reasons for warranting exclusion from this population will be documented prior to database lock.
Safety analysis set	All participants who receive any portion of study intervention. Participants will be analyzed according to the intervention they actually received.
PK analysis set	All participants who receive any portion of study intervention and have at least one post-dose concentration value.

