2.2. Secondary Endpoints

- GC IL-2 change from Day 15 (first day of GC) pre-GC to Day 15 post GC.

GC IL-2 will be log transformed prior to calculating the change.

- Change from baseline in IEL density in duodenum biopsy after 2-week GC (at Day 29).

The biopsy will be performed at screening and Day 29, or ET visit. The Baseline is the last non-missing IEL density at screening.

- Incidence and severity of TEAEs as assessed by the CTCAE.

See [Section 2.5.1](#).

- Incidence and titer of KAN-101 ADA.

Positive of ADA will be assessed at Days 1, 7, 29, 42 or early termination (ET) visit.

- Plasma concentration of KAN-101, and associated KAN-101 parameters: AUC_{inf}, AUC_{last}, C_{max}, T_{max} and t_{1/2}.

Parameter	Definition	Method of Determination
AUC _{last}	Area under the plasma concentration-time profile from time 0 to the time of the last quantifiable concentration (C _{last})	Linear/Log trapezoidal method
AUC _{inf}	Area under the plasma concentration-time profile from time 0 extrapolated to infinite time	AUC _{last} + (C _{last} /K _{el}), where C _{last} is the predicted plasma concentration at the last quantifiable time point estimated from the log-linear regression analysis
C _{max}	Maximum plasma concentration	Observed directly from data
T _{max}	Time to first occurrence of C _{max}	Observed directly from data.
t _{1/2} ^a	Terminal elimination half-life	Log _e (2)/K _{el} , where K _{el} is the terminal Phase rate constant calculated by a linear regression of the loglinear - concentration time- curve. Only those data points judged to describe the terminal log-linear decline will be used in the regression

- a. If data permits.

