4.3. Methods to Manage Missing Data

If a PK concentration value is below Lower Limit of Quantification (LLOQ), that concentration value will be treated as 0 for all analysis. For IL-2, values below LLOQ will be treated as $\frac{1}{2}$ LLOQ. Other missing values will not be imputed for safety, efficacy and PK endpoints.

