5.2.6. PK Parameters

PK parameters listed in [Section 2.2](#) (AUC_{inf}, AUC_{last}, C_{max}, T_{max}, and t_{1/2}) will be descriptively summarized by treatment group with number of observations, mean, SD, min, 1st, 2nd and 3rd quartiles, max, GM, and %CV for PKAS. No GM and %CV for T_{max}.

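### The SAP's PK set drops the protocol's post-dose condition, and separately no rule stops Cmax being read from a dosing day that lacks its end-of-infusion sample

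*SAP*

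**What the plan says.** **Who is in the PK set.** Protocol Section 9.3: "All participants who receive any portion of study intervention and have at least one post-dose concentration value". The protocol synopsis agrees: participants who "received any portion of study intervention and have at least one post-dose drug concentration value". SAP Section 3: "All participants who receive any portion of study intervention and have at least one concentration value". The post-dose condition is gone, and SAP Section 7 (Changes from Protocol) does not mention it.

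**How values are handled.** SAP Section 4.3 says of a PK concentration below the LLOQ "that concentration value will be treated as 0 for all analysis", with no distinction by sampling time. It adds: "Other missing values will not be imputed for safety, efficacy and PK endpoints".

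**How Cmax is obtained.** The parameter table in SAP Section 2.2 gives the method for Cmax and Tmax as "Observed directly from data". No minimum set of samples is required. The proviso that data must permit derivation is attached to the half-life only.

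**What is reported.** SAP Section 5.2.6 says of the PK parameters that they "will be descriptively summarized by treatment group with number of observations, mean, SD, min, 1st, 2nd and 3rd quartiles, max, GM, and %CV for PKAS", and exempts only Tmax from the geometric mean and %CV.

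**When blood is drawn.** Per the protocol's Table 1, on Days 1 and 7: before dosing, at the end of infusion, and then "Additional sampling will be done at 2.5 hours (±5 minutes) and 4 hours (±5 minutes) after infusion start".

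**The concern.** There are two gaps, and they are independent of each other.

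1. *Set membership.* Under the SAP's definition a participant who received part of an infusion and has only a pre-dose sample belongs to the PK set. That sample should be unquantifiable, because previous tolerance-inducing therapy for celiac disease is an exclusion criterion. It therefore counts as 0. It is also the largest observed value, so Cmax is 0.

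2. *Parameter derivation.* Of the four samples per PK day, only the end-of-infusion draw lies near the peak. If it is missed, the rule for Cmax still returns a number: the largest of what remains. Leaving the missed concentration unimputed does not make Cmax itself missing.

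In both cases the SAP, applied as written, puts a number into the summary where there is no information on the peak. Cmax and the AUCs are secondary endpoints, summarised in about 26 KAN-101 participants, so a single record can be visible in the geometric mean.

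**Working it through.** The plan states no figure on this point to reproduce. The check is on the size of the consequence.

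**Inputs**
- Infusion of about 30 min (Protocol 6.1.1).
- Next samples at 150 and 240 min after infusion start (Protocol Table 1).
- Mean half-lives of 3.74 to 36.8 min (Protocol 2.2.3, Study KAN-101-01); on the order of 30 min (Protocol 4.3). The 20-min row below is an assumed intermediate value.
- 26 participants per arm (SAP 1.3).
- CV defined as SD/mean (SAP 4.2).
- Assumptions: first-order one-compartment decline; otherwise equal Cmax values for the mean and geometric-mean ratios; a CV of 30% before the faulty record.

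**Step 1. Pre-dose sample only.** Cmax = 0. The arithmetic mean falls by 1/26 = 3.8%. The geometric mean is 0 as a product, and not computable on the log scale. AUClast is not affected in the same way: it runs to the last quantifiable concentration, and here there is none.

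**Step 2. Missed end-of-infusion sample.** The fraction of the end-of-infusion concentration left at 2.5 h is f = 2^(−(150 − 30)/t½). With one such record in 26, the geometric mean is multiplied by f^(1/26) and the arithmetic mean by 1 − (1 − f)/26.

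| t½ (min) | f at 2.5 h | Geometric mean × | Arithmetic mean × |
|---|---|---|---|
| 36.8 | 10.4% | 0.917 | 0.966 |
| 30 | 6.25% | 0.899 | 0.964 |
| 20 | 1.6% | 0.852 | 0.962 |
| 3.74 | about 2 × 10⁻¹⁰ | if set to 0: zero or undefined | 0.962 |

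The 4 h sample is lower still (1.9% at 36.8 min, 0.8% at 30 min), so the 2.5 h value becomes Cmax. If it is below the LLOQ, Cmax is 0. The range is therefore 0 to about 10% of the true value.

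**Step 3. Effect on %CV at t½ = 30 min.** Take 25 records with mean 1 and SD 0.30, and one at 0.0625.
- Mean = (25 + 0.0625)/26 = 0.964.
- Sum of squares = 24 × 0.09 + 25 × (0.036)² + (0.901)² ≈ 2.160 + 0.033 + 0.813 = 3.005.
- SD = √(3.005/25) = 0.347.
- CV = 0.347/0.964 ≈ 36%, against the assumed 30%.

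**Step 4. AUClast at t½ = 30 min** (linear up, log down, peak scaled to 1, all post-dose values quantifiable).
- With the end-of-infusion point: 15.0 + 40.6 + 2.4 = 57.9.
- Without it: ½ × 150 × 0.0625 + 2.4 = 7.1, about 12% of the former.

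**Step 5. Does restoring the post-dose condition cure both gaps?** No. A participant with 2.5 h and 4 h samples meets the protocol's definition too, so Step 2 is unchanged. If Cmax is set to missing instead, the summary uses 25 records and the distortion disappears.

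**The case against.** The case on the other side is substantial, and parts of it stand.

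- *The set definition does not cause the missed-sample problem.* This stands. A reader might infer from the SAP's looser wording that it is what lets a missed peak sample through. The documents do not support that: such a participant qualifies under either definition.
- *The loss of precision can be made to look dramatic.* A reader might compute a geometric CV, which would go from 30% to about 68%. The SAP defines CV as SD/mean, and on that definition the figure is about 36%.
- *Existing rules already cover part of this.* AUClast stops at the last quantifiable value, and half-life uses only points judged to lie on the terminal decline. A broad restriction of the zero rule would therefore add little. These rules do not cover Cmax, or an AUClast built without the peak.
- *Protocol Section 9.4.5 defers to sponsor data standards, which may say when Cmax is not reported.* Possible, but they are not in the documents. SAP Section 4.2 includes geometric means only where appropriate, yet Section 5.2.6 lists them without that condition.
- *No planned comparison is harmed.* A reader might infer that a Day 1 versus Day 7 exposure comparison is at risk. Neither document plans one. Medians and quartiles are also reported, and one record barely moves them.
- *Prolonged infusions differ.* Appendix 9 of the protocol describes a rate of 2 hours per dose after a reaction. If the whole infusion ran at that rate, the 2.5 h sample would come 30 min after its end and hold 50% of the peak at a 30-min half-life and 57% at 36.8 min. The 0-to-10% range applies to standard infusions only.
- *Placebo zeros.* Summaries are by treatment group, so unquantifiable placebo samples cannot distort the KAN-101 figures. Limiting PK summaries to the KAN-101 arm would correct no error in those figures.

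**Conclusion.** The point holds as two minor defects. First, the SAP departs from the protocol's PK set without listing the departure, and its own rules then give a Cmax of 0 to a participant with only an unquantifiable pre-dose sample. Second, the SAP has no rule for a dosing day without an end-of-infusion sample. Read literally, it yields a Cmax of 0 to about 10% of the true value after a standard 30-min infusion. One such record in 26 lowers the geometric mean by about 8% (half-life 36.8 min) to 10% (30 min), more at shorter half-lives, and makes it zero or undefined if the value is set to 0.

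These sizes rest on one-compartment decline, the documented half-lives and an assumed 30% CV. The LLOQ and the frequency of missed draws are not given. The draws are made in clinic, and Protocol Section 8.5 asks for every effort to sample on time, so the problem may never arise. The documents do not support reading this as a threat to the trial's conclusions: PK is summarised descriptively, and the primary analysis does not use it.

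**What to change.** 1. In SAP Section 3, restore the protocol's definition: "All participants who receive any portion of study intervention and have at least one post-dose concentration value".
2. In SAP Section 2.2 or 4.3, add that for any dosing day without a valid end-of-infusion sample, Cmax, Tmax and the AUCs are not derived: they are set to missing, and the concentrations are listed. Define validity against the actual end of the infusion, so that prolonged infusions are covered.

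Both changes are needed, since neither replaces the other: the first aligns the set with the protocol, and the second deals with the missed peak sample. The cost is SAP wording and slightly fewer evaluable PK profiles, one fewer per missed draw (25 instead of 26 for a single miss). No change to sampling or to the protocol is required.

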4. GENERAL METHODOLOGY AND CONVENTIONS

4.1. Hypotheses and Decision Rules

This protocol is designed to establish the superiority of KAN-101 to PBO for the primary endpoint of the change in Vh:Cd ratio at Day 29. The null hypothesis is that there is no difference between KAN-101 and PBO, and the alternative hypothesis is that there is a significant difference between KAN-101 and PBO. KAN-101 will be considered superior to PBO with the change in Vh:Cd ratio at Day 29, at the interim look, if the difference is statistically significant at the 2-sided 0.003 level. Even if significance is reached at the interim analysis, no decision to stop the trial will be made unless a safety concern arises. Statistical significance will be evaluated at the end of study at the 2-sided 0.049 level.

4.2. General Methods

In general, count and percent will be presented for categorical variables. Number of observations, mean, standard deviation (SD), minimum (min), 1st, 2nd, 3rd quartiles, and maximum (max) will be presented for continuous variables. The coefficient of variation (CV, defined as SD/Mean; %CV=100*CV), geometric mean (GM), and geometric mean ratio (GMR) will also be included, where appropriate. Graphics will be used to present the data.

4.2.1. Analyses for Continuous Endpoints

For continuous endpoints, the change from baseline will be analyzed by timepoint using analysis of covariance (ANCOVA) model with treatment as a factor, baseline as a covariate. For endpoints without baseline, analysis of variance (ANOVA) model with treatment as a factor will be used for the analysis. Comparison of KAN-101 to PBO (providing LSM of the treatments, LSM of the treatment difference, p-value and 95% CI) will be generated.

4.3. Methods to Manage Missing Data

If a PK concentration value is below Lower Limit of Quantification (LLOQ), that concentration value will be treated as 0 for all analysis. For IL-2, values below LLOQ will be treated as $\frac{1}{2}$ LLOQ. Other missing values will not be imputed for safety, efficacy and PK endpoints.

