**Table 1. Schedule of Assessments**

Abbreviations used in this table may be found in Appendix 12 .	Scr.	Treatment Period				Gluten Challenge (Day 15 to 28)			Biopsy	FU	ET	Notes
Visit Identifier	V1	V2	V3	V4	V5	V6	V7	V8	V9	ET		
 
• Day relative to start of study intervention (Day 1).
 
• See Section 8.4.3 for follow-up AE and SAE assessments.
 
• D16 and D21 are phone call visits (See Section 8.1.1) for collection of AEs and concomitant medications.
 

Type (Site or Phone Call)	Site	Site	Site	Site	Site	Phone	Phone	Site	Site	Site		
Study Day (D)	Up to -42 days	D1	D4	D7	D15	D16	D21	D29	D42	ET		
Visit Window (days)					+2	±2	+3	+3				
ADA sample		X		X				X	X	X		
 
• D1 & D7 samples should be taken pre-dose (at least 5 minutes prior to infusion).
 

Plasma biomarker (includes IL-2) sample		X	X	X	X			X	X	X		
 
• See Section 8.2.2 for additional information.
 
• D1, D4, and D7 samples should be taken pre-dose (at least 5 minutes prior to infusion) and 4 hours post end of infusion ± 15 minutes. Day 15 sample should be collected prior to GC and at 4 hours (± 15 minutes) after GC.
 
• A single sample is collected on D29, D42, and ET.
 
• Participants who withdraw from treatment and do not receive 3 full doses should not have plasma samples collected at D15, D29, and D42.
 

ADA – Anti-Drug Antibody; AE – Adverse Event; CDS – Celiac Disease Symptom Diary; CeD – Celiac Disease; D – Day; DGP IgG – Deamidated Gliadin Peptide, Immunoglobulin G; ECG – Electrocardiogram; eDiary – Electronic Diary; EGD – Esophagogastroduodenoscopy; ET – Early Termination; FU – Follow Up; GC – Gluten Challenge; GFD – Gluten Free Diet; HBV – Hepatitis B Virus; HCV – Hepatitis C Virus; HIV – Human Immunodeficiency Virus; HLA – Human Leukocyte Antigens; IL-2 – Interleukin-2; IV – Intravenous; PGIC – Patient Global Impression of Change; PGIS – Patient Global Impression of Severity; PK – Pharmacokinetics; PRO – Patient Reported Outcome; SAE – Serious Adverse Event; Scr – Screening; tTG, IgA – Tissue Transglutaminase Immunoglobulin A; V – Visit

CONFIDENTIAL

CT02-GSOP Clinical Protocol Template Phase 1 2 3 4 (14 April 2023)

Page 26

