#### Study KAN-101-01

In Study KAN-101-01 administration of KAN-101 was effective at inducing T-cell tolerance (Murray et al, 2023):

- Three doses of KAN-101, administered 3 days apart, at 0.15, 0.3 and 0.6 mg/kg dose levels was effective in inducing T cell tolerance to gliadin. KAN-101 treated participants exhibited minimal change or a decrease in the gliadin-specific T-cell response following GC while placebo patients exhibited an increase in the gliadin-specific T-cell response following GC.

CONFIDENTIAL

- KAN-101 also modified the immediate immune reaction upon ingestion of gluten by CeD participants in a dose-dependent manner. Participants treated with 3 doses of 0.6 mg/kg KAN-101, administered 3 days apart, exhibited lower median plasma IL-2 levels within hours of GC compared to placebo or 0.15 and 0.3 mg/kg KAN-101 dose levels.

KAN-101 demonstrated an acceptable safety and tolerability profile after single and multiple doses at all dose levels tested in KAN-101-01. There were no deaths, SAEs, or Grade 3 TEAEs observed. TEAEs were consistent with CeD participants upon gluten ingestion (ie, nausea, emesis, abdominal pain, headache, and diarrhea). No clinically relevant trends were observed for changes in vital signs, physical examination, laboratory tests, or ECG results. There were no meaningful correlations between the frequency of TEAEs and study drug dose level. There was an increased frequency of participants who experienced GI AEs in the total drug-treated group than in the placebo group in KAN-101-01. No MTD of KAN-101 was identified and no meaningful safety differences were observed among treatment groups during the study.

Data from the KAN-101-01 study suggests rapid elimination with mean half-life ranging from 3.74 to 36.8 minutes across 0.15 mg/kg to 1.2 mg/kg doses, following single or repeat IV infusions of KAN-101. The mean KAN-101 maximum exposure ( $C_{max}$ ) and systemic exposure (AUC) appeared to exhibit approximate dose proportionality across 0.15 to 1.2 mg/kg dose range. With repeat dosing, there was no accumulation of KAN-101 which was in concordance with the rapid elimination.

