1.3. Sample Size

A sufficient number of participants will be screened to achieve approximately 52 treated participants (26 per study arm). The sample size calculation is based on the primary efficacy estimand and its endpoint, changes from baseline in the ratio of Vh:Cd at Day 29 visit. With

an overall 2-sided type I error rate of 5%, the study will have approximately 94% power under a sample size of 26 participants per arm to detect a treatment difference in LSM of 0.50 in change in ratio of Vh:Cd between treatment arms, assuming that the common standard deviation is 0.5 and the difference between the means is 0.5. To adjust for multiple looks, the O'Brien-Fleming adjustment is applied to control overall type I error rate to ensure that the overall Type I error rate remains at 5%. The interim analysis will be evaluated at significance level 0.003 and the final look will be evaluated at significance level 0.049.

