5.2.1.1. Main Analysis

Log transformed GC IL-2 change from pre GC to post GC at Day 15 will be analyzed using ANCOVA model as described in Section 4.2.1 based on Estimand 2 (see Section 1.1.2) for the BS. The LSM change (log transformed), LSM difference of LSM change (log transformed) between KAN-101 and PBO, 95% CI, and p-value will be presented. Exponentially transformed values for LSM, LSM difference, 95% CI will be presented as well.

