5.2.1.2. Sensitivity/Supplementary Analysis

The above analysis will also be performed for the log transformed GC IL-2 for the analysis sets stated in Section 5 as a supplementary analysis.

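### Half-LLOQ substitution for IL-2 has no censored-data check: if clearly more than half of KAN-101 post-challenge values are below LLOQ, the ratio drifts towards 1 and its 95% CI is too narrow

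*SAP*

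**What the plan says.** SAP 4.3 gives the rule: "For IL-2, values below LLOQ will be treated as" half the LLOQ. SAP 5.2.1.1 then specifies the model: "Log transformed GC IL-2 change from pre GC to post GC at Day 15 will be analyzed using ANCOVA model". SAP 4.2.1 defines that as a "model with treatment as a factor, baseline as a covariate". The result is reported as a ratio: "Exponentially transformed values for LSM, LSM difference, 95% CI will be presented as well".

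For sensitivity, SAP 5.2.1.2 says "The above analysis will also be performed for the log transformed GC IL-2 for the analysis sets stated in Section 5". The table in SAP Section 5 and Appendix 1 show that these sets are the PPS and the SAS. The population changes and the LLOQ rule does not. The SAP plans no censored-data analysis, rank-based analysis or alternative substitution value for IL-2, and no count of values below LLOQ.

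The protocol gives no LLOQ rule. Its Schedule of Assessments provides one post-challenge IL-2 sample on Day 15: "Day 15 sample should be collected prior to GC and at 4 hours (± 15 minutes) after GC". On the expected direction, Protocol 2.2.3 reports that participants given three 0.6 mg/kg doses in KAN-101-01 "exhibited lower median plasma IL-2 levels within hours of GC compared to placebo" or the lower dose levels. Neither document gives the LLOQ, the IL-2 SD or the share of values expected below the limit.

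**The concern.** A value below LLOQ is known only to lie under the limit. Replacing it with one constant sets a floor on the log scale: a post-challenge IL-2 of 0.4 times LLOQ and one of 0.05 times LLOQ both become 0.5 times LLOQ. If the drug lowers IL-2, more values reach that floor on KAN-101 than on placebo. The floor then holds up the KAN-101 mean, and the identical substituted values shrink the residual variance, so the interval narrows around a displaced centre.

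At stake is the size of the IL-2 effect and its stated precision. IL-2 is a secondary endpoint with its own estimand, and Protocol 4.3 cites IL-2 data in support of the dosing regimen. An understated ratio with a falsely tight CI could mislead comparison across doses or studies. The planned sensitivity analyses would agree with the main result because they share the rule.

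**Working it through.** The plan states no IL-2 figure, so there is none to reproduce.

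**Inputs from the documents.** Half-LLOQ rule (SAP 4.3); ANCOVA of log change on treatment and baseline (SAP 4.2.1, 5.2.1.1); 26 per arm (SAP 1.3); one post-challenge sample (Protocol Schedule of Assessments). Baseline is read as the pre-challenge log value.

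**Assumptions, not in the documents.** IL-2 is log-normal, with a post-challenge log SD of 1.2 (0.8 and 1.6 were also tried) and a placebo median of 2, 4, 8 or 16 times LLOQ. Pre-challenge values are mostly below LLOQ. Substitution there largely cancels from the treatment difference because baseline is a covariate.

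**Step 1: where the estimate settles.** Let m = ln(median/LLOQ), s = log SD, and p = Φ(−m/s), the share below LLOQ. After substitution the mean log value, relative to LLOQ, is

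E = p·ln(0.5) + m·(1 − p) + s·φ(m/s).

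The reported ratio tends to exp(E for KAN-101 − E for placebo).

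Worked case: s = 1.2, placebo at 8 × LLOQ, true ratio 0.125.
- Placebo: m = 2.079, p = 0.042, E = 2.071.
- KAN-101, median at the LLOQ: m = 0, p = 0.50, E = −0.347 + 0.479 = 0.132.
- Reported ratio: exp(0.132 − 2.071) = 0.144, against a true 0.125.

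The same formula with s = 1.2:

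| Placebo median / LLOQ | True ratio | KAN-101 below LLOQ | Reported ratio | Reported / true |
|---|---|---|---|---|
| 8 | 0.25 | 28% | 0.256 | 1.02 |
| 8 | 0.125 | 50% | 0.144 | 1.15 |
| 4 | 0.25 | 50% | 0.289 | 1.16 |
| 8 | 0.0625 | 72% | 0.094 | 1.51 |
| 4 | 0.125 | 72% | 0.190 | 1.52 |
| 2 | 0.125 | 88% | 0.289 | 2.31 |
| 8 | 0.02 | 94% | 0.068 | 3.41 |

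In the limit the ratio becomes (LLOQ/2) divided by the placebo geometric mean: 0.125, 0.063 or 0.031 for placebo at 4, 8 or 16 × LLOQ. If every KAN-101 value and no placebo value is below LLOQ, substituting the LLOQ instead of half of it doubles the reported ratio.

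**Step 2: CI coverage, by simulation at 26 per arm, s = 1.2.**
- Up to about 50% of KAN-101 below LLOQ: about 92 to 96%. At 50% itself it was 93.5% (placebo at 8 × LLOQ) and 92.3% (4 × LLOQ).
- About 70%: roughly 64 to 78%; for example 68.6% with placebo at 4 × LLOQ and a true ratio of 0.125.
- About 88%: 7%. With 21 per arm it was 18%.

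The CI also tightens. With placebo at 8 × LLOQ, the upper limit divided by the lower falls from 3.87 with no effect to 2.68 at a true ratio of 0.02.

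The SD matters. Across SDs of 0.8 to 1.6, coverage with 55 to 84% of KAN-101 below LLOQ ran from 95% down to 7%. The 95% came from SD 0.8, placebo at 16 × LLOQ and 61% below LLOQ.

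**Step 3: the test.** With no treatment effect, rejection at the 5% level was 3.8 to 5.5% over all settings.

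**Step 4: the left-censored alternative.** A Tobit fit without covariate, placebo at 8 × LLOQ, s = 1.2:

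| True ratio | KAN-101 below LLOQ | Tobit | Half-LLOQ |
|---|---|---|---|
| 0.125 | 51% | 0.123 | 0.142 |
| 0.05 | 78% | 0.052 | 0.086 |
| 0.02 | 93% | 0.022 | 0.070 |

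Tobit coverage was 93.5 to 95%. In the last row about 15% of trials had every KAN-101 value below LLOQ (0.93^26 = 0.15), and no Tobit ratio exists for those.

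**The case against.** A reader might infer that the rule makes the IL-2 ratio wrong in any case, or as soon as the drug brings IL-2 down to the assay limit. The documents do not support that. A median at the limit puts about half the values below it, where the bias is modest and coverage is still about 92 to 95%. The rule in SAP 4.3 is a contingency, set beside a similar one for PK, and does not show that most treated values will be unquantifiable. The prior IL-2 data cited in the protocol give direction only. The 88% case needs a placebo median of only 2 × LLOQ, at which 28% of placebo values are unquantifiable too. All of this stands, and it makes the point conditional.

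A reader might also infer a risk of a false claim of benefit. The error runs the other way: heavy censoring pulls the ratio towards 1, and the test of no difference keeps its level. The decision rule in SAP 4.1 concerns Vh:Cd only.

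The problem would be partly visible already. SAP Section 5 plans minimum, quartiles and median by arm; with half of an arm below LLOQ, all the lower ones would equal half the LLOQ. That would flag the problem without correcting the ratio or giving the counts.

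Finally, Tobit should not simply replace the ANCOVA. It relies on log-normality below the limit, was tested here only on log-normal data, and gives no point estimate when an arm is fully censored. At 88% below LLOQ that has probability 0.876^26 = 3% with 26 per arm, or 0.876^21 = 6% with 21. This supports its use as a sensitivity analysis rather than as the main one.

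**Conclusion.** The concern holds conditionally. When clearly more than half of KAN-101 post-challenge values are below LLOQ, the planned ratio depends on the LLOQ, understates the effect (by a factor of about 1.5 at 72% below and 2.3 at 88%), and carries a CI that is too narrow. With about a third or fewer below LLOQ the effect is negligible. These sizes rest on log-normal IL-2 with log SD 1.2 and a placebo median of 2 to 8 × LLOQ. The SD, the true ratio and the number analysed all move the coverage figures. Whether the condition will arise cannot be judged from the documents. The inference of no difference and the primary endpoint are untouched. The gap is that no planned IL-2 analysis gives a usable ratio if censoring proves heavy.

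**What to change.** Keep the half-LLOQ ANCOVA as the main IL-2 analysis and make these additions to the SAP before unblinding:

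1. In 5.2.1 and Appendix 1, report the number and percentage of IL-2 values below LLOQ by arm and time point, and state the LLOQ.
2. In 5.2.1.2, name a left-censored (Tobit) regression of log post-challenge IL-2 on treatment and log pre-challenge IL-2, with an indicator for a pre-challenge value below LLOQ. Post-challenge values below LLOQ enter as censored. With the pre-challenge value as covariate, the treatment term targets the same difference as the change-score ANCOVA.
3. State in advance that the ratio is read from this model when more than about half of an arm is below LLOQ.
4. If all values in an arm are below LLOQ, report only a bound on the ratio, with a rank-based test. If that arm is KAN-101, its geometric mean lies below the LLOQ, so the observed ratio lies below the LLOQ divided by the placebo geometric mean.

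The cost is a short SAP addition, one standard procedure and one table, with no new data. The downsides are one extra analysis, a somewhat wider CI, reliance on log-normality below the limit, and no point estimate when an arm is fully censored. Where censoring is light the two methods agree and nothing is lost.
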